In this regard, evidence-based approaches, such as strengths-based care management, could be added to BIs to enhance efficacy; however, to be feasible in the ED and VHA, service delivery needs to be modified to minimize demands on VHA providers. Peers are ideal candidates for providing alcohol BIs and post-ED strengths-based assistance in the form of peer mentoring because of their shared experiences with patients. Peers can serve as role models and provide emotional support resulting in greater self-efficacy, healthy behavior change, and linkage to needed services.^{9,10} *Therefore, the objective of this proposed study is to conduct a hybrid randomized controlled trial (RCT) to determine the efficacy of an peer-delivered alcohol intervention starting in the ED with peer-delivered brief alcohol advice, combined with a continuing 6-session program of post-ED strengths-based peer mentorship, compared to standardized brief advice in the ED only, to facilitate reduction in risky drinking and linkage and engagement in primary and/or specialty alcohol treatment services care, if needed – an **Alcohol Peer-Mentor Intervention (APM; n=225)**, compared to **Brief Advice in the ED only (BA; n=225)** condition. The primary specific aims are to:*

Aim 1: Determine the efficacy of the ED APM intervention compared to BA on subsequent TLFB drinking frequency reports, including number of drinking days per month, number of drinks per drinking day, and number of binge drinking days at 3-, 6-, and 12-months post-baseline. **Hypothesis:** Veterans with hazardous drinking who are randomly assigned to APM will have significantly greater reductions in alcohol use as measured by TLFB reports, compared to those assigned to BA at 3-, 6-, and 12-month follow-ups.

Aim 2: Determine the impact of the APM intervention on linkage to primary and specialty alcohol treatment services care, mental health symptoms and functioning at 3-, 6-, and 12-months post-baseline. **Hypothesis:** Veterans with hazardous drinking who are randomly assigned to APM will be significantly more likely to link and engage in primary, specialty care, and other VHA supportive services and to have improvements in mental health symptoms and functioning.

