It is important to explore the mechanisms of action that explain how the APM intervention influences change. The **secondary specific aim is to determine the mediators** (e.g., motivation to change, self-efficacy, coping, perceived helpfulness of social support) of the effect of the intervention and linkage on subsequent alcohol use and alcohol-related consequences. An **exploratory aim is to conduct structured qualitative interviews** in order to understand barriers and facilitators of implementation of the APM

intervention in the ED with Veteran participants, clinicians, and peer mentors.

RESEARCH PLAN

Background

Extent of Hazardous and Harmful Drinking in Veterans. The recent Institute of Medicine (IOM) report highlights alcohol as a key problem needing intervention and/or treatment among military personnel, in general, and Veterans, in particular. Hazardous drinking occurs along a spectrum of severity from occasional over-consumption at levels that could be damaging to one's health, to engaging in risky behaviors (e.g., driving). Harmful drinking includes the development of an alcohol use disorder (AUD), which is characterized by a series of alcohol-related problems. Harmful and hazardous drinking, including binge drinking,¹¹ and alcohol-

Drinking Definitions

- **Harmful drinking:** Use of alcohol that causes complications (includes abuse and dependence, problem drinking)
- **Hazardous drinking:** Use of alcohol that increases risk for complications (includes risky or at-risk drinking)
- **Non-hazardous drinking:** Use of alcohol without clear risk of complications (includes beneficial use)

Source: World Health Organization

related problems are particularly common among Veterans.^{5,12-15} The VHA serves a high proportion of Veterans with alcohol and comorbid mental health problems.^{12,13,16} The percentage of Veterans enrolling in VHA with mental health problems, including substance abuse, has dramatically increased with the influx of Veterans from Operation Iraqi Freedom/Operation Enduring Freedom (OIF/OEF). Official VHA data for the first half-million of these Veterans seeking care in VHA documented that 56% presented with a mental health problem, including substance abuse. This is a dramatic increase from Veterans in earlier wars. Hazardous and harmful drinking (AUDs) are common

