Self-Report Healthcare Service Use. We will use the Treatment Services Review (TSR) to measure health services use, which has adequate reliability and validity.⁷⁰ We will also access VHA electronic health data, focusing on primary care; substance abuse treatment, and psychiatric treatment services (including mutual aid groups such as AA, receiving detox services, and other substance abuse care settings).

Health Care Utilization using Medical Records. In the last year of the study, a review of participants' medical records will be conducted to determine diagnoses, service use (i.e., ED visits, hospitalizations, primary and specialty care) for one year pre- and post-entry into the study. We will use these data to assess agreement with self-report service use, particularly VHA services, and seek to understand sources of discrepancy. Data will be accessed through CPRS, Corporate Data Warehouse (CDW), and the Joint Legacy Viewer (JLV).

Health Functioning. One item from the SF-12⁷¹ will assess perceived health functioning, which are accepted

Table 2: Study Measures	Instrument	When*	#Min
Primary Outcomes			
Alcohol Consumption	TLFB	B, 3,6,12	20
Secondary Outcomes			
Alcohol Consumption	AUDIT	S, 3, 6, 12	5
Alcohol Consequences	SIP	B, 3, 6, 12	5
Health Service Use	TSR/CPRS	B, 3,6, 12	10-15
Health Functioning	SF-12	S, 3,6,12	
Depressive Symptoms	PHQ-9	B, 3,6,12	
PTSD Symptoms	PC-PTSD-5	B, 3,6,12	
Substance Use	ASSIST	B, 3, 6, 12	
Opioid Misuse	COMM	B, 3, 6, 12	
Problem Severity	BAM	B, 3,6,12	
Individual Factors			
Demographics	SAOM	S/B	5-10
Motivation to Change/Readiness	Rulers	B, 3, 6, 12	
Self-Efficacy	Ruler	B, 3, 6, 12	
Social Factors			
Social Support	mMOS	B, 3, 6, 12	10
Peers Services	WAI-SR	3	
Intervention Interaction	Metric, Sentiment		0

*S=Screen; B=Baseline, 3-month, 6-month, 12-month follow-ups

Veterans.²⁹

Substance Use

Alcohol, Smoking, and Substance Involvement Screening Test (ASSIST) is a structured interview for alcohol, tobacco, cannabis, stimulants, sedatives and opioid use disorders in general medical settings. We will use a brief screening for tobacco use (ASSIST-LITE) and the full ASSIST version 3 to measure use of all other substances.

Opioid Misuse: a modified version of the Current Opioid Misuse Measure (COMM) will assess extent of opioid medication misuse.

Individual Factors

Demographics: Background characteristics assessed include: age, sex, marital status, education, employment, income, legal history, deployment history, etc.⁷⁷

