parameter estimates that account for missing data under the missing-at-random assumption.⁸⁹ We will look for non-random attrition, and if we find, for example, attrition rates to depend on a baseline covariate, we will include this covariate in the model. If we find attrition to depend on treatment use or ideation at prior assessments, we will utilize an appropriate pattern mixture model or multiply impute data based on an appropriate pattern mixture model assumptions based on the observed missing data pattern.⁸⁸

Aim 1: Determine the efficacy of the ED APM intervention compared to BA on TLFB drinking frequency reports at 3-, 6-, and 12-months post-baseline. **Hypothesis:** Veterans with hazardous drinking who are randomly assigned to APM will have significantly greater reductions in total TLFB drinking frequency reports, compared to those assigned to CBA.

Data Analysis for Aim 1: The primary purpose of Aim 1 is to examine the impact of the intervention on frequency of drinking per TLFB interview. This outcome will likely follow the assumptions required for linear regression model, but we will adjust the model type as needed. Assuming this is the case; we will use a linear mixed-effects model and estimate the treatment effect as the difference in the time-averaged TLFB frequencies over the year of follow-up. Because reduction in problem alcohol use is of primary interest, the analysis will model change-scores from baseline in the response variable as dependent variable, and the independent variables will include the baseline values of the response variable, time in months since randomization, and the treatment group indicator. The parameter estimate of the treatment group indicator will estimate the time-averaged treatment effect. *In a second model, we will include an interaction of time by treatment group indicator to formally test the possibility that the effect varies over time. Models will include a random effect for which specific peer/clinician a participant was assigned.*

Aim 2: Determine the impact of the APM intervention on linkage to primary and specialty alcohol treatment services care, mental health symptoms and functioning at 3-, 6-, and 12-months post-baseline, compared to BA. **Hypothesis:** Veterans with hazardous drinking who are randomly assigned to APM will be significantly more likely to engage in primary, specialty care, and other VHA supportive services and to have improvements in mental health symptoms and functioning.

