Data Analysis for Aim 2: The focus of Aim 2 is to study intervention effects on secondary outcome of frequency of primary care and mental health specialty care visits (as two separate outcomes) from the TSR, calculated as an average number of visits per month during each follow-up period. Similar to Aim 1, analyses will generally use a mixed effect model framework. As described above, initial analyses will examine the distribution of outcome measures over follow-up in order to select an appropriate model (e.g. Poisson regression or a related method for counts of visits). Our analysis strategy will parallel Aim 1 in terms of the independent variables, *random effect for peer/brief advice, focus on time-average treatment effects, and additional modeling of interactions of group and time.*

Secondary Aim will determine the mediators (e.g., motivation to change, self-efficacy, coping, social support) of the effect of the intervention and linkage on subsequent alcohol use and alcohol-related consequences. **Hypothesis:** The effect of randomization to APM compared to BA on the primary outcomes (i.e., alcohol consumption and consequences) will be mediated by differences between groups in motivation to change, self-efficacy, and perceived helpfulness of peer support.

Data Analysis for Secondary Aim: *In order to establish temporal ordering, we will examine whether level of the hypothesized mediators at 3 and 6 months post-baseline mediates the effect of random assignment on 6- and 12-month measures of the three primary outcomes of alcohol use behaviors.^{90,91} We will first determine the whether study condition is associated with the hypothesized mediators over the first six months of follow-up and check for a direct effect of the mediators at 3 and 6 months on alcohol use as measured at 6- and 12-months follow-up. We will estimate the indirect effect of the intervention on alcohol use through the mediators and conduct significance testing of this effect using macros created by Preacher and Hayes.⁹²*

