Data Analysis for Exploratory Aim: Interviews will be audiotaped and transcribed verbatim for content. We will conduct analyses. We will use a rapid data analysis process, a technique used when there is a need for targeted, actionable information.⁹³ The research team will read early transcripts independently, and, in an iterative process, meet to develop and refine the coding scheme and code definitions, including developing new codes from the data based on ongoing data analysis. We will document code definitions, data interpretation, and analytic decisions in memos. Once the research team has agreed on codes and code definitions, Drs. [name] and [name], and the research supervisor, will independently review and code transcripts, meeting regularly to compare coding results, and resolving discrepancies through a consensus process. If coding definitions are refined during this process, the coders will recode transcripts already coded. Once data are coded, we will use QSR NVivo 10 software to organize the data. The study team will meet regularly to discuss code summaries and memos, developing findings with a focus on barriers and facilitators to implementation and potential testable implementation strategies. Members of the study team have used similar methods in a study of the acceptability of peer support interventions in Michigan NG soldiers.^{94,95}

Power and Sample Size Calculations

Of 450 participants randomized, we expect that at least 80% of participants will be retained (n=360). We conservatively have estimated power without accounting for methods that will allow inclusion of participants with partial follow-up data because this benefit will be off-set to an unknown degree by the additional parameters estimated in a mixed effects model. All power analyses used G*Power 3.1.9 software and a two-sided $\alpha = .05$. We calculated power based on several potential outcome measure distributions. If a linear model is appropriate, which we expect to be the case for the primary outcome of total AUDIT scores, we achieve 80% power to detect an effect size (Cohen's d) of 0.30. This is a relatively modest and reasonable effect size for studies of SBIRT models of alcohol brief interventions. For an outcome with a count distribution and assuming a mean level in controls of 1 (e.g., an average of 1 alcohol-related treatment visit in a follow-up period), we achieve 80% power to detect an incidence rate ratio of 0.75 or 1.34 under a Poisson framework.

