personally, in order to fully ensure participant privacy).

Exclusion Criteria for RCT. (1) individuals currently active in or having recently completed alcohol or other substance abuse treatment in the past 3 months; (2) patients currently in or having received peer services in the past 3-months per self-report screening.

After providing written informed consent to participate in the RCT component of the study, completing the baseline assessment, eligible participants will be randomized into Alcohol Peer-Mentored (APM) Intervention condition or the Brief Advice (BA) condition. Participants in both conditions will receive brief personalized feedback advice from an ED clinician or the peer mentor. For those in the APM condition, following the brief advice session, the peer will set up the first post-ED contact with the participant. All participants in both conditions will receive a community and VA resource guide covering health care and community assistance options.

All participants who choose to participate in the study will complete a baseline assessment and three additional follow-up assessments (i.e., 3-, 6-, 12-months post baseline).

Sources of Research Material. Data will be obtained by means of interviews and self-report inventories specifically for research purposes. Primary sources of data for this study will be gathered from an initial eligibility screening assessment, baseline assessment, and follow-up assessments (i.e., 3, 6, and 12 months post baseline). To supplement self-report measures, we will abstract VA records for health services information such primary care visits, substance abuse treatment, outpatient mental health service utilization.

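### Aim 2 asks about linkage to specialty alcohol treatment, but its analysis gives that care no separate prespecified result and leaves mental health specialty care undefined

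*Combined protocol and SAP*

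**What the plan says.** - **The aim.** Specific Aims and the Data analyses section both set Aim 2 as the effect of APM on "linkage to primary and specialty alcohol treatment services care, mental health symptoms and functioning". The hypothesis in Specific Aims is that APM participants will be "significantly more likely to link and engage in primary, specialty care, and other VHA supportive services".
- **The analysis.** Data Analysis for Aim 2 gives the focus as "frequency of primary care and mental health specialty care visits (as two separate outcomes) from the TSR", each expressed as average visits per month in each follow-up period. The model parallels Aim 1. No outcome is named for alcohol or substance-use treatment, and mental health specialty care is not defined there or elsewhere.
- **The data.** Self-Report Healthcare Service Use describes the Treatment Services Review (TSR) and adds VHA electronic data. Besides primary care, these data are to cover "substance abuse treatment, and psychiatric treatment services (including mutual aid groups such as AA, receiving detox services, and other substance abuse care settings". Sources of Research Material lists "primary care visits, substance abuse treatment, outpatient mental health service utilization" for abstraction from VA records. Health Care Utilization using Medical Records covers one year before and after study entry and says "We will use these data to assess agreement with self-report service use".
- **Power.** For a count outcome, Power and Sample Size Calculations uses as its example "an average of 1 alcohol-related treatment visit in a follow-up period".

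**The concern.** The aim and its analysis name different things. The aim names specialty alcohol treatment; the analysis names mental health specialty care. A reader cannot tell from the documents whether a visit to an alcohol programme counts in the second outcome, or in neither.

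This care is close to the trial's rationale. Specific Aims gives, as one of several reasons for the trial, that single-session ED interventions have not increased alcohol treatment-seeking in people with more serious problems. The section on alcohol brief interventions adds that few who needed specialty treatment received it. Under the plan as written, a rise in the pooled count could occur with no change in alcohol treatment, and a real rise in alcohol treatment could be diluted by other visits. Alcohol visits could be separated out later, but visit types, data source and model would then be chosen with the data in hand, although General analytic approach promises hypotheses set in advance. The Secondary Aim also refers to linkage, again with no defined variable.

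**Working it through.** The point rests on comparing texts. No calculation is needed to establish it.

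**1. Does any reading of mental health specialty care give alcohol treatment its own result?**

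- *Inclusive reading.* The Background describes "mental health problems, including substance abuse", though that phrase concerns diagnoses and not services. In Self-Report Healthcare Service Use, the parenthesis placing AA, detox and other substance-use settings follows psychiatric services. Alcohol treatment is then analysed, but only inside a broader count.
- *Exclusive reading.* The same sentence, before its parenthesis, lists substance-use treatment as a separate item beside psychiatric care. Sources of Research Material also lists it beside outpatient mental health care. Alcohol treatment then falls outside the second outcome. Alcohol care given in primary care, which the section on alcohol brief interventions allows for, would be counted among all primary care visits.

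Neither reading isolates specialty alcohol treatment.

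**2. Is it covered elsewhere?** General analytic approach mentions other addictions treatment only as an adjustment variable or potential mediator. The power section uses an alcohol-related visit as an example, but the Aim 2 analysis does not list it.

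**3. Can the outcome be built?** Yes. The TSR is scheduled at baseline, 3, 6 and 12 months, and VHA records cover the year after entry. Patients with substance-use treatment in the previous 3 months are excluded, so a later contact is new relative to that window.

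**4. How sparse might it be? (Illustration only.)** Inputs from the plan: 450 randomized, 80% retained, so 360, or 180 per arm; two-sided alpha 0.05; rate ratio 1.34; control mean 1.

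First, the plan's own 80%. With log(1.34) = 0.2927, the standard error under the alternative is sqrt(1/180 + 1/(180 × 1.34)) = 0.0985. Under the null at the control rate it is sqrt(2/180) = 0.1054.

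- Null variance: Φ((0.2927 − 1.96 × 0.1054)/0.0985) = 0.81, which agrees with the plan.
- Wald: Φ(0.2927/0.0985 − 1.96) = 0.84.

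Replacing 180 by 180 × mean, with lower control means that are assumptions:

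| Control mean | Power, null variance | Power, Wald |
|---|---|---|
| 1 (plan) | 81% | 84% |
| 0.5 (assumed) | 50% | 56% |
| 0.25 (assumed) | 27% | 32% |

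These are Poisson figures without overdispersion. They show only that a rarer outcome would be estimated less precisely.

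**The case against.** **The inclusive reading may be what was meant.** The documents elsewhere place peers who work on substance-use problems within mental health services. On that reading alcohol treatment is analysed within a broader outcome, in keeping with the commitment in General analytic approach to few outcomes, and a one-line definition might seem enough. This stands as a reason not to call alcohol treatment unanalysed. It does not remove the gap, because a pooled count cannot answer a question about alcohol treatment.

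**The boundary is less tidy than a split into two care types.** Alcohol treatment can be delivered in primary care. That also stands, but such visits are mixed with all other primary care visits.

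**Simply adding an outcome would bring its own problems.** This stands in full, on four counts:
- The planned adjustment for other addictions treatment, carried into Aim 2 through the parallel model, would adjust the new outcome for part of itself.
- Peer training includes progress notes in the medical record. If study sessions are charted, they could be counted as contacts in one arm only.
- The status of AA and detox is open.
- A cumulative yes/no outcome does not use partial follow-up as the mixed model does.

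**Stronger readings to avoid.** A reader might infer that the trial will have no data on alcohol treatment; the measures sections say otherwise. A reader might infer that the stated 80% power is wrong at ratio 1.34; it reproduces. A reader might infer that the added outcome is shown to be underpowered; the documents give no control rate from which to show that.

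**Conclusion.** The concern holds as a mismatch between an aim and its prespecified analysis. Specialty alcohol treatment, named in the linkage part of Aim 2, has no separate between-arm result. It is either pooled with other mental health visits or, apart from alcohol care in primary care, not analysed.

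The conclusion does not depend on which reading was intended or on any assumed rate. Its reach is limited to a secondary outcome whose data are already planned. It should be corrected before the outcome data are examined.

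**What to change.** In Data Analysis for Aim 2:

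1. Keep the two existing outcomes, and define mental health specialty care to exclude substance-use treatment visits.
2. Add one prespecified secondary outcome, specialty alcohol or substance-use treatment, taken from the TSR supplemented by VHA records: any contact over follow-up, with the visit count per period in the planned mixed model as supportive.
3. State that study peer sessions and study brief advice do not count as contacts, and whether mutual aid and detox do.
4. State how TSR and VHA records are combined when they disagree. The medical-records section at present uses the records to check agreement with self-report.
5. State how participants with missed follow-ups are handled. For example, VHA records can cover the full year for VHA care.
6. Do not apply the adjustment for other addictions treatment to this outcome.
7. Report the estimate with its confidence interval.

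**Cost.** SAP wording and one more secondary outcome in a plan meant to limit them; no new data collection. The outcome may be sparse, so a null result would be inconclusive. If the inclusive reading was intended, the mental health visit count will be lower. Care outside VHA still rests on self-report.
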